4.8. Safety Analyses

The safety and tolerability of treatment will be assessed by summarizing the following:

- AEs
- Treatment-emergent adverse events (TEAEs)
 - By PT
 - By SOC
 - By maximum severity
 - By considered to be related to investigational produce by investigator
- Serious Adverse Events (SAEs)
- AE leading to discontinuation
- Suicide-Related Thoughts and Behaviors
- Vital signs and weight
- Laboratory measurements
- Electrocardiograms (ECGs)

All safety analyses will be based on the safety population. AE rates will be summarized by treatment group and overall, and will be broken down by severity, seriousness and relation to study drug. Change of MRI, C-SSRS, physical examinations, vital signs, ECG

and standard laboratory results will be summarized with means, standard deviations, medians and ranges for continuous variables and with counts and percentages for categorical variables. Statistical tests are not planned for safety.

4.8.1. Adverse Events

An AE is defined as any untoward medical occurrence in a subject who is administered a medicinal product and that does not necessarily have a causal relationship to the treatment. All AEs will be included in the data listings. Verbatim terms on case report forms will be mapped to preferred terms and system organ classes (SOC) using the Medical Dictionary for Regulatory Activities (MedDRA) (version 19.1).

A Treatment Emergent Adverse Event (TEAE) is defined as an adverse event that occurs on or after the treatment dose. TEAE summary will be displayed by treatment. Unless otherwise specified, summaries that are displayed by SOC and preferred terms will be ordered alphabetically by SOC, and within each SOC, preferred terms will also be ordered alphabetically. Summaries of the following types will be presented:

- Subject incidence of TEAEs by MedDRA SOC and preferred term.
- Subject incidence of TEAEs by MedDRA SOC, preferred term, and severity. Severity will be recorded as deemed by investigator. At each level of subject summarization, a subject is classified according to the highest severity if the subject reported one or more events.
- Subject incidence of study drug related TEAEs by MedDRA SOC and preferred term.
- Subject incidence of TEAEs by descending incidence of preferred terms.
- Subject incidence of serious TEAEs by MedDRA SOC and preferred term, if applicable.
- Subject incidence of TEAE leading to early termination by MedDRA SOC and preferred term, if applicable.

For each subject and for each adverse event, the duration of the event will be calculated as:

$$\text{Duration of AE} = \text{AE stop date} - \text{AE start date} + 1$$

The duration of AEs will be displayed in the data listing.

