4.3 Follow-up Period

4.3.1 Visit 13: 1st Follow-up Visit (Week 30)

The first follow-up visit, Visit 13, will occur approximately 12 weeks (\pm 7 days) after Visit 12. During this visit, the following assessments/procedures should be performed:

- Measure vital signs (sitting blood pressure, pulse, breathing, and temperature) and weight.
- Perform a complete physical examination.
- Measure 12-lead ECG.
- Record any changes in concomitant medications.
- Record any adverse events, if applicable.
- The following questionnaires will be completed: ADAS-Cog (see Appendix 2), MMSE (see Appendix 3), CDR-SOB (see Appendix 4). NPI (see Appendix 5), GDS (see Appendix 6), ADCS-ADL (see Appendix 7) and C-SSRS (see Appendix 8).

- Collect blood and urine samples for hematology, serum chemistry, pregnancy test (only for women of childbearing potential), biomarker analysis and urinalysis.
- Perform MRI scan including FLAIR and T2- weighted gradient-echo sequences.

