4.3.2 Visit 14: Final Follow-up Visit (Week 52)

The final follow-up visit, Visit 14, will occur approximately 22 weeks (\pm 7 days) after Visit 13. During this visit, the following assessments/procedures should be performed:

- Measure vital signs (sitting blood pressure, pulse, breathing, and temperature) and weight.
- a complete physical examination.
- Measure 12-lead ECG.
- Record any changes in concomitant medications.
- Record any adverse events, if applicable.
- Perform The following questionnaires will be completed: ADAS-Cog (see Appendix 2), MMSE (see Appendix 3), CDR-SOB (see Appendix 4). NPI (see Appendix 5), GDS (see Appendix 6), ADCS-ADL (see Appendix 7), and C-SSRS (see Appendix 8).
- Collect blood and urine samples for hematology, serum chemistry, pregnancy test (only for women of childbearing potential), biomarker analysis and urinalysis.
- Perform MRI scan including FLAIR and T2- weighted gradient-echo sequences.

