4.4. Baseline and Postbaseline Definition

Table 5 describes the rules for determining the patient population and baseline and postbaseline observations for study and type of analysis.

Table 5. Patient Population with Baseline and Postbaseline Definitions by Type of Analysis

Study Period/Analysis	Patient Population	Baseline Observation	Postbaseline Observation(s)
Treatment Period			
Primary Efficacy analyses	ITT Population with a baseline and at least 1 postbaseline observation	Visit 3	Visit 13
TEAEs	Safety Population	All Visits 1-3	All Visits 3.01-14
Serious Adverse Events, Discontinuations due to Adverse Events	Safety Population	N/A	
C-SSRS analyses	Patients with a baseline and at least 1 postbaseline C-SSRS assessment	All Prior History: Visits 1-3 including	All Visits 3.01-14
Treatment-emergent abnormal laboratory values	Safety Population with normal laboratory values at all nonmissing baseline visits (with respect to direction being analyzed) and who have at least 1 postbaseline observation	Low: Minimum from Visits 1-3 High: Maximum from Visits 1-3 Abnormal: All Visits 1-3	Low: Minimum from Visits 3.01-14 High: Maximum from Visits 3.01-14 Abnormal: All Visits 3.01-14
Treatment-emergent immunogenicity	Safety Population	Visit 3	All Visits 3.01-14
Treatment-emergent changes in temperature and weight	Safety Population with a baseline and at least 1 postbaseline observation	Low: Minimum from Visits 1-3 High: Maximum from Visits 1-3	Low: Minimum from Visits 3.01-14 High: Maximum from Visits 3.01-14
Treatment-emergent changes in blood pressures, pulse, and ECGs	Safety Population with a baseline and at least 1 postbaseline observation	Low: Last nonmissing from Visits 1-3 High: Last nonmissing from Visits 1-3	Low: Minimum from Visits 3.01-14 High: Maximum from Visits 3.01-14
Continuous safety analyses	Safety Population with a baseline and at least 1 postbaseline observation	Last of Visits 1-3	All scheduled visits 3 < Visits ≤ 14

ECGs = electrocardiograms; eCRF = electronic case report form; ITT = intent-to-treat; N/A = not applicable; TEAEs = treatment-emergent adverse events

Note: Visit 3.01 indicates the first unscheduled visit occurring after Visit 3 and prior to Visit 4.

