As guidance for determination of important medical events see the ‘WHO Adverse Reaction Terminology – Critical Terms List’. These terms either see or might be indicative of a serious disease state. Such reported events warrant special attention because of their possible association with a serious disease state and may lead to more decisive action than reports on other terms.

4.8.3. *Clinical Laboratory Evaluation*

Abnormal laboratory findings without clinical significance (based on the investigator's judgment) should not be recorded as adverse events; however, laboratory value changes requiring therapy or adjustment in prior therapy are considered adverse events. Adverse events will be reviewed continuously throughout the study.

Laboratory results (hematology, serum chemistry and urinalysis) will be presented in data listing. Abnormal values will be flagged as high or low relative to the local lab normal ranges, where applicable. Values that are deemed as abnormal, clinically significant will also be flagged.

Laboratory results will be summarized using descriptive statistics at baseline and post-dose. Changes from baseline will also be summarized. Only non-missing assessments at baseline and post-dose will be analyzed.

Any clinically significant lab abnormalities will be determined by the Principal Investigator and will be reported in the AE table summaries.

4.8.4. *Suicide-Related Thoughts and Behaviors*

Suicidal ideation, suicidal behavior, and self-injurious behavior without suicidal intent occurring during treatment, based on the C SSRS, will be summarized by treatment. In particular, for each of the following events, the number and percent of patients with the event will be enumerated by treatment: completed suicide, nonfatal suicide attempt, interrupted attempt, aborted attempt, preparatory acts or behavior, active suicidal ideation with specific plan and intent, active suicidal ideation with some intent to act without specific plan, active suicidal ideation with any methods (no plan) without intent to act, nonspecific active suicidal thoughts, wish to be dead, and self-injurious behavior without suicidal intent.

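### The TEAE and C-SSRS incidence tables treat all time to Week 52 as one treatment window although infusions end at Week 18, so no event-incidence table isolates dosing

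*SAP*

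**What the plan says.** Protocol 3.5.1 places one infusion at each of Visits 3 to 12 (Weeks 0 to 18). The protocol then separates a treatment period (section 4.2) from a follow-up period (section 4.3). Only two visits are scheduled after the last infusion: "The first follow-up visit, Visit 13, will occur approximately 12 weeks" after Visit 12, and "The final follow-up visit, Visit 14, will occur approximately 22 weeks" after Visit 13.

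The SAP does not carry this division into its event tables:

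- SAP 4.8.1: "A Treatment Emergent Adverse Event (TEAE) is defined as an adverse event that occurs on or after the treatment dose". No closing day is given. On layout it says "TEAE summary will be displayed by treatment". The listed tables are by system organ class and preferred term, severity, relatedness, seriousness and early termination. None is split by study period.
- SAP 4.4, Table 5: the post-baseline window for both the TEAE row and the C-SSRS row is "All Visits 3.01-14". Both rows sit under the heading "Treatment Period", and the table has no follow-up heading.
- SAP 4.8.4: suicidal ideation, suicidal behaviour and self-injury are those "occurring during treatment, based on the C SSRS, will be summarized by treatment".

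Under protocol 3.6.3, AEs are collected at every visit, and the C-SSRS is done at Visits 3, 6, 9, 12, 13 and 14.

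**The concern.** Two different kinds of time are added together in each incidence figure. Up to Week 18 subjects are being infused and are asked about AEs every two weeks. After Week 18 they receive no infusions, and people with dementia and their caregivers must recall events over 12 and then 22 weeks.

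Safety is a primary objective and no safety tests are planned (SAP 4.8), so these descriptive tables carry the safety conclusion. Two things are at stake. First, the during-treatment label in 4.8.4 does not describe the window that Table 5 assigns to it. Second, a reader who wants the incidence of events while patients were being infused will find no prespecified table that gives it. If harm is concentrated around the infusions, background events in follow-up raise incidence in both arms and reduce the visible contrast.

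**Working it through.** **Schedule, from the protocol.** The first infusion is at Week 0, with nine more at 2-week intervals: 9 × 2 = Week 18. Visit 13 is at 18 + 12 = Week 30 and Visit 14 at 30 + 22 = Week 52. These match the stated weeks. Time after the last infusion is 52 − 18 = 34 weeks. So 18/52 = 34.6% of the window is dosing and 34/52 = 65.4% is follow-up. With 11 per arm and no dropout, that is 11 × 18 = 198 and 11 × 34 = 374 subject-weeks per arm.

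**Gaps between assessments.**

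| | Weeks 0–18 | After Week 18 |
|---|---|---|
| AEs | 2 weeks | 12, then 22 weeks |
| C-SSRS | 6 weeks | 12, then 22 weeks |

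**Effect on the contrast if harm is confined to dosing.** Let H_A and H_P be the cumulative hazards to Week 18 in the active and placebo arms, and H_F the follow-up hazard as recorded, equal in both arms. Then

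RD(0–52) = [1 − exp(−H_A − H_F)] − [1 − exp(−H_P − H_F)] = exp(−H_F) × RD(0–18).

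Since exp(−H_F) = 1 − follow-up event risk, the proportional shrinkage of the risk difference equals the follow-up event risk, whatever the hazard ratio during dosing.

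**Size.** The documents give no event rates, so all rates here are assumptions. Shrinkage = 1 − exp(−rate × capture × 34), where capture is the share of follow-up events that is recorded.

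| Assumed background per week | 50% capture | 100% capture |
|---|---|---|
| 0.01 (any event) | 1 − exp(−0.17) = 16% | 1 − exp(−0.34) = 29% |
| 0.04 (any event) | 1 − exp(−0.68) = 49% | 1 − exp(−1.36) = 74% |
| 0.001 (single term) | 1 − exp(−0.017) = 2% | 1 − exp(−0.034) = 3% |
| 0.003 (single term) | 1 − exp(−0.051) = 5% | 1 − exp(−0.102) = 10% |

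The upper two rows imply a 52-week placebo incidence of 1 − exp(−0.52) = 41% to 1 − exp(−2.08) = 88% with full capture. That suits a total over all events, not a row for one preferred term.

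**Worked example** (assumed: placebo 18-week risk 20%, hazard ratio 3 during dosing and 1 afterwards, full capture).

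- Weeks 0–18: active 1 − 0.8³ = 48.8%, placebo 20.0%. The difference is 28.8 points and the risk ratio 2.44, or about 5.4 v 2.2 of 11 subjects.
- The follow-up factor is 0.8^(34/18) = 0.656.
- Weeks 0–52: active 1 − 0.512 × 0.656 = 66.4%, placebo 1 − 0.8 × 0.656 = 47.5%. The difference is 18.9 points and the risk ratio 1.40, or about 7.3 v 5.2 of 11.

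**The same example with the hazard ratio of 3 persisting to Week 52.** Active 1 − (0.8 × 0.656)³ = 85.5% v 47.5%. The difference rises from 28.8 to 38.0 points. The direction therefore depends on whether the excess risk outlasts dosing. It also depends on the background: at an assumed 30% placebo 18-week risk, a persisting hazard ratio of 3 takes the difference from 35.7 to 31.1 points, because most subjects in both arms have by then had an event.

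**The case against.** The strongest reply is that the pooled table is valid and that little is lost. Several parts of it stand.

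- Dilution is conditional. The plan itself allows for effects that outlast dosing: the primary efficacy endpoint is 12 weeks after the last infusion, and protocol 7.3 requires related SAEs to be reported however long after the last dose. A reader might infer that the SAP window hides infusion-related harm. The documents do not support this, because they do not say when any harm would stop.
- The primary safety endpoint counts subjects with treatment-related events. Background events judged unrelated do not enter it, so the any-event shrinkage above does not measure the effect on that endpoint. The related-event table does, however, use the same open window.
- It would be wrong to say that no safety output shows the dosing period. Change in C-SSRS is summarised at Visits 6, 9 and 12 (SAP Table 3), and vital signs and ECG at each post-dose time point (SAP 4.8.5 and 4.8.6). The protocol synopsis also promises safety summaries by group and visit. The gap is confined to event-incidence tables.
- Both arms follow the same blinded schedule, so the change in ascertainment does not by itself favour either arm.
- All AEs are listed for about 22 subjects, so a reader could split them by date. That split would be made after unblinding, with a cut-off chosen then; prespecifying it avoids this.

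None of this answers the mislabelled C-SSRS window or the missing dosing-period incidence table.

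**Conclusion.** The point holds as a matter of labelling and presentation, and it is worth acting on because the remedy is cheap. Without any assumption: 65% of the window called treatment falls after the last infusion, the wording of SAP 4.8.4 is untrue for events arising in follow-up, and no event-incidence table isolates the dosing period.

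The effect on the between-arm contrast is an assumption, not a finding. It requires excess harm confined to dosing and equal follow-up hazards. On that basis the risk difference shrinks by about 16% to 74% for any-event totals (0.01 to 0.04 per week, 50% to 100% capture) and by about 2% to 10% for individual terms (0.001 to 0.003 per week). If excess risk persists, the long window can enlarge the difference. The 52-week table is therefore incomplete on its own, not wrong, and should not be replaced. No p-value is affected.

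**What to change.** In SAP Table 5, 4.8.1 and 4.8.4:

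1. Define a dosing period by AE onset, from the first infusion to a prespecified number of days after the subject's last infusion, and a follow-up period from then to Visit 14. The 30 days in protocol 7.3 is one available choice; for a subject who receives all infusions it ends at about Week 22.3 (18 + 30/7).
2. Show the TEAE, related-TEAE, serious-TEAE and C-SSRS incidence tables for each period beside the pooled 52-week column. If space or sparsity prevents this at preferred-term level, do it at least for the any-event and related-event totals.
3. Assign C-SSRS events by assessment visit, because the follow-up form asks about the time since the last visit and the Visit 13 recall would straddle a 30-day cut-off.
4. Restrict the during-treatment wording in 4.8.4, and the period heading in Table 5, to the dosing part.
5. Footnote the assessment interval in each period, separately for AEs and C-SSRS.

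The cost is SAP wording and extra columns. AE onset dates and visit numbers are already collected. The drawback is sparser cells at 11 per arm, which is why the pooled column stays.

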4.8.2. Potential Hypersensitivity Events (Serious Adverse Events)

A serious adverse event (SAE) is any AE or suspected adverse reaction that in the view of either the investigator or Sponsor, results in any of the following outcomes:

- Death

- A life-threatening AE: it is defined as an AE or suspected adverse reaction that in the view of the investigator or Sponsor, its occurrence places the patient or subject at immediate risk of death. It does not include an AE or suspected adverse reaction that, had it occurred in a more severe form, might have caused death.
- Inpatient hospitalization or prolongation of existing hospitalization
A persistent or significant incapacity or substantial disruption of the ability to conduct normal life function.
- A congenital anomaly/birth defect
- Important medical events that may not result in death, be life-threatening, or require hospitalization may be considered serious when, based upon appropriate medical judgment, they may jeopardize the patient or subject and may require medical or surgical intervention to prevent one of outcomes listed in the above definition

Life threatening:

An adverse event or suspected adverse reaction is considered “life-threatening” if, in the view of either the investigator or sponsor, its occurrence places the patient or subject at immediate risk of death. It does not include an adverse event or suspected adverse reaction that, had it occurred in a more severe form, might have caused death.

Hospitalization:

Any adverse event leading to hospitalization or prolongation of hospitalization will be considered as ‘serious’, UNLESS at least one of the following exceptions is met:

- the admission results in a hospital stay of less than 24 hours OR
- the admission is pre-planned (i.e., elective or scheduled surgery arranged prior to the start of the study)

However, it should be noted that invasive treatment during any hospitalization may fulfill the criteria of ‘medically important’ and as such may be reportable as a SAE dependent on clinical judgment.

Disability means a substantial disruption of a person’s ability to conduct normal life functions.

Important medical event:

As guidance for determination of important medical events see the ‘WHO Adverse Reaction Terminology – Critical Terms List’. These terms either see or might be indicative of a serious disease state. Such reported events warrant special attention because of their possible association with a serious disease state and may lead to more decisive action than reports on other terms.

4.8.3. *Clinical Laboratory Evaluation*

Abnormal laboratory findings without clinical significance (based on the investigator's judgment) should not be recorded as adverse events; however, laboratory value changes requiring therapy or adjustment in prior therapy are considered adverse events. Adverse events will be reviewed continuously throughout the study.

Laboratory results (hematology, serum chemistry and urinalysis) will be presented in data listing. Abnormal values will be flagged as high or low relative to the local lab normal ranges, where applicable. Values that are deemed as abnormal, clinically significant will also be flagged.

Laboratory results will be summarized using descriptive statistics at baseline and post-dose. Changes from baseline will also be summarized. Only non-missing assessments at baseline and post-dose will be analyzed.

Any clinically significant lab abnormalities will be determined by the Principal Investigator and will be reported in the AE table summaries.

4.8.4. *Suicide-Related Thoughts and Behaviors*

Suicidal ideation, suicidal behavior, and self-injurious behavior without suicidal intent occurring during treatment, based on the C SSRS, will be summarized by treatment. In particular, for each of the following events, the number and percent of patients with the event will be enumerated by treatment: completed suicide, nonfatal suicide attempt, interrupted attempt, aborted attempt, preparatory acts or behavior, active suicidal ideation with specific plan and intent, active suicidal ideation with some intent to act without specific plan, active suicidal ideation with any methods (no plan) without intent to act, nonspecific active suicidal thoughts, wish to be dead, and self-injurious behavior without suicidal intent.

In addition, the number and percent of patients who experienced at least one of various composite measures will be presented and compared. These include suicidal behavior (completed suicide, non-fatal suicidal attempts, interrupted attempts, aborted attempts, and preparatory acts or behavior), suicidal ideation (active suicidal ideation with specific plan and intent, active suicidal ideation with some intent to act without specific plan, active suicidal ideation with any methods [no plan] without intent to act, non-specific active suicidal thoughts, and wish to be dead), and suicidal ideation or behavior.

4.8.5. *Vital Signs*

Vital signs will be summarized using descriptive statistics at baseline and at each post-

dose time point. Changes from baseline will also be summarized.

4.8.6. *Electrocardiogram*

ECG parameters (numeric) will be summarized using descriptive statistics at baseline and at each post-dose time point. Changes from baseline will also be summarized.

4.9. Interim Analysis and Data Monitoring

An unblinded interim safety analysis was done when there the first 4 subjects complete Visit 4 at Week 2 by an independent safety monitor. Change of vital sign, concomitant medications and adverse events(AEs) were evaluated to monitor the safety of the AstroStem.

Vital sign measured at Visit 3 and 4 were within normal ranges and no AEs were reported. In addition, all 4 subjects were found to be taking concomitant medications before and after administration of the treatment.

4.10. Handling of Dropouts or Missing Data

No imputations will be made for missing values.

4.11. Subgroup Analysis

There are no planned subgroup efficacy analyses.

4.12. Multiple Comparison/Multiplicity

No adjustments for multiplicity or multiple testing will be made.

5. Changes to Protocol-Specified Analyses

No changes to protocol-specified analyses are planned.

6. References

Alzheimer's Association. 2016 Alzheimer's disease facts and figures. Alzheimers Dement. 2016 April;12(4):459-509.

7. Appendices

